- Gingival Index (*GI*, Loe and Silness) at surgical site(s). A periodontal probe will be swept around the tooth sulcus at a depth of 1-2 mm. The examiner will determine the status of tissue health. A single score will be recorded for buccal and lingual/palatal surface of each tooth examined as follows:

0 = healthy tissue

1 = mild inflammation but no bleeding

2 = moderate inflammation with bleeding

3 = severe inflammation with a tendency toward spontaneous bleeding

- Width of keratinized tissue (KT) will be measured at tooth site(s) at the mid-buccal aspect from the mucosal margin to the mucogingival junction.
- Width of attached tissue (AT) will be calculated by subtracting PD from KM
- Tissue Thickness (TT1 and TT2) at the buccal mucosa will be measured during the surgical visit by horizontal transmucosal probing (sounding the bone) using an endodontic reamer after local infiltration of anesthetic prior to surgical site preparation. TT1 and TT2 will be measured at 2 mm and 5 mm from the mucosal margin, respectively.

Clinical photographs of the tooth site (s) will be obtained with one digital SLR camera.

Randomization: two groups (Participants will be randomized like the flip of a coin to one of the two groups listed.) Randomly generated treatment groups will be printed on note cards and placed in sealed opaque envelopes. Once the patient consents to participate in the study an envelope is opened, and the patient is then offered the allocated treatment regimen.

Group 1: will receive vestibular incision supraperiosteal tunnel access (VISTA) + Acellular Dermal Matrix (ADM) graft around teeth with gingival recession and lack of KT.

Group 2: will receive sulcular tunnel access + Acellular Dermal Matrix (ADM) graft around teeth with gingival recession and lack of KT.

Surgical visit (Visit 1): Patients will be anesthetized via infiltration around recipient tooth/teeth site(s). Study surgeon will confirm measurements taken at baseline with relation to width of keratinized tissue (KT) and evaluate thickness of mucosa (TT1 and TT2) as described above. Surgeon will then measure the recipient site to determine the size of graft needed and ensure that surgical treatment will avoid any vital structures. Soft tissue grafting procedures will include local anesthesia, monitoring of vital signs (bp, HR, O2 sat). Study surgeons will follow standard-of-care procedures for soft tissue as follows:

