The tooth/teeth site(s) will be prepared utilizing a papilla-sparing, sulcular incision extending one tooth mesial and distal to the tooth/teeth site(s) to be treated and split-thickness flap elevated on buccal aspect leaving a thin periosteum as recipient bed. Extension of the flap apically and laterally to allow for adequate coronal advancement and coverage of the ADM graft material will be insured. Mesio-distal and apico-coronal dimensions will be measured at recipient site the ADM material trimmed after hydration and washing per package instruction to equal dimensions and uniform thickness will be performed. Exact AMD graft dimensions will be measured with a calibrated UNC-15 periodontal probe and its thickness will be measured using a caliper prior to placement within the suprapariosteal pouch at the recipient site. ADM graft will be secured in position and overlying flap secured in a coronal position with multiple suture techniques.

Table 2: Tunneling and ADM technique

	
Pt. presents with Miller Class II and III recession defects.

---	---

	
Incision made on the front of each tooth to be treated.

	
Elevation of the flap with blunt dissection to necessary level.

	
Insertion of acellular dermal matrix.¹⁵

	
Positioning of acellular dermal matrix with sutures overlying root surfaces.

	
Flap positioned at the desired level and sutured into place.

	
One month post-operative evaluation of healing.

To help guard against possible infection, a pre-surgical antibiotic loading dose will be dispensed and prescriptions for relief of post-surgical discomfort, follow-up antibiotics and written home care instructions will be provided.

Follow up visits: The surgical sites will be examined at 1 week (visit 2) and 2 weeks (visit 3) after surgical visits and loose sutures will be removed. Exams will then be scheduled at 1 month (visit 4), 3 months (visit 5), 6 months (visit 6), and 1 year (visit 7).

During these follow up visits the following will take place:

1. Medical history review (all visits)
2. Assess for adverse events experience (all visits)
3. Intra-oral photographs: (all visits)
4. Clinical measurements:

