The width of keratinized tissue (KT) will be assessed at visits 4, 5, 6 and 7. Tissue thickness (TT1 and TT2) will be evaluated at visits 5, 6 and 7. Clinical measurements will be collected by calibrated examiners. Measurements from all visits will be compared to baseline in order to evaluate the progression of healing over time up to 12 months post-op.
5. Patient satisfaction survey
This survey will be performed at visits 2 and 4 using a visual analogue scale (VAS) based questionnaire regarding esthetic appearance, pain, swelling, bruising, effects on daily activities. Esthetic evaluation by the patient will also be assessed at visits 6 and 7.
6. Pink Esthetics Score (PES)
This standardized assessment of esthetics will be performed at visits 6 and 7 by blinded, calibrated examiners.
7. Study participation and satisfaction survey to be completed at final study visit (visit 7)

Inclusion/Exclusion Criteria:

Inclusion Criteria	Exclusion Criteria
English speaking	Non-English speaking
At least 18 years old	Less than 18 years old
Must be a patient of the UAB Dental School	Smokers/tobacco users (>10 cigarettes/day)
Able to read and understand informed consent document.	Patients with systemic pathologies or conditions contraindicating oral surgical procedures or adversely affecting wound healing.
One or more adjacent teeth (up to four) with Miller class I or II gingival recession defects and ≤ 2mm of KT at each site to be treated.	Presence of active periodontal disease or radiographic interproximal bone loss or tooth malposition, which would yield a Miller class III or IV categorization for the recession defect.
Presence of periodontally healthy, non-carious neighboring teeth, healthy implants, or edentulous ridges on either side of the involved site(s)	Presence of frenulae or other soft tissue anomalies at the site(s) to be treated that, in the opinion of the investigators, will interfere with successful access and treatment of the soft tissue defects.
No anticipated need for restorative care at the teeth to be treated during the study period.	Previous soft tissue grafting at the site(s) to be treated

--	--

Group Table:

Group	Treatment	Number of participants
Group 1	Vestibular incision suprapariosteal tunnel access (VISTA) + Acellular Dermal Matrix (ADM) graft	20
Group 2	Sulcular tunnel access + Acellular Dermal Matrix (ADM) graft	20

3. Study Background:

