Soft tissue grafting for root coverage and alteration of the quality of gingival tissue surrounding teeth was originally described in 1956 using a Lateral Pedicle Flap.¹ Since that time, myriad techniques and materials have been described to improve clinical outcomes and patient acceptance.²⁻⁶ Systematic reviews and meta-analyses have concluded that root coverage and KT gain at sites with Miller class I or II defects could be reliably achieved with the use of allogeneic donor tissue as well as autogenous connective tissue harvested from a patient’s palate.⁷⁻⁹ Use of a tunnel technique has also been shown to demonstrate decreased post-operative discomfort when compared with a standard coronally advanced flap.¹⁰ Recently, there has been renewed interest in vestibular incisions, originally described in 1912¹¹, for the coronal advancement of gingival tissues with the use of graft materials due to purported decrease in post-operative discomfort and healing time.

Given the increase in the number of procedures performed, this study seeks to compare two established tunneling technique procedures with the use of allogeneic soft tissue graft materials to evaluate clinical and patient-centered outcomes to determine if there are any notable differences in post-operative healing and clinical outcomes associated with each technique.

4. Outcomes Measures

Outcomes will be measures by an evaluation of the following:

- Percentage previously visible root surface that has been covered by gingiva at 6- and 12-months following grafting with VISTA and sulcular tunnel access with ADM as compared to the baseline data.
- KT width as measured in mm by practitioner at 6- and 12-month following grafting with VISTA and sulcular tunnel access with ADM
- Change in tissue thickness evaluated with gentle intrasulcular probing and level of transparency of the grafted sites at 6 and 12 months.
- Practitioner-assessed esthetic outcomes using a standardized pink esthetic scale (PES) at 6 and 12 months postoperatively.
- Patient-assessed esthetic outcomes of root coverage and soft tissue appearance at 6 and 12 months post-operatively
- Patient centered outcomes including pain, bleeding, swelling, change in daily activities at 1 week and 1 month postoperatively, see attached Visual Analog Scale (VAS)

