- Group sample sizes of 20 and 20 achieve 92% power to detect non-inferiority using a one-sided, two-sample t-test. The margin of non-inferiority is -1.0. The true difference between the means is assumed to be 0.1. The significance level (alpha) of the test is 0.025. The data are drawn from populations with standard deviations of 1.0 and 1.0.

- Regarding patient-centered outcomes, there is not adequate data available to complete an accurate sample size analysis to determine the proper N, therefore in this respect this study serves as a pilot study.

5. Benefits:

Benefits of this project for individual participants include enhancing periodontal soft tissue health and thus decreasing the risks of dentinal sensitivity, radicular (root) caries (tooth decay), and tooth root structure wear as well as a reduction in progressive recession and periodontal attachment loss at the tooth sites to be treated. Information gained from this research may be used by investigators to facilitate a healthier environment around teeth with gingival recession and a lack of keratinized tissue (KT) with therapies that are well-accepted with low post-operative morbidity.

6. Risks

The only risks associated with this protocol involve potential loss of confidentiality and randomization. Precautions will be taken to ensure that patient confidentiality is maintained. All records will be assigned identifying alphanumeric codes and the list linking identifying PHI to patient data will be kept on a password protected computer and destroyed immediately after statistical analysis is completed. All surveys and consent documents will have assigned non-identifying, alphanumeric codes and the list linking personal information and patient data will be kept on a password protected computer and destroyed immediately after data analysis have been completed. Intra-oral photos will also be assigned alphanumeric codes that link with codes assigned to the demographic data collection form and consent documents. Photos will be stored as digital images on encrypted computers in the department of Periodontology. The photos will be used in the publication and presentations.

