Regarding the randomization risk, patients will be assigned to a group by chance, which may prove to be less effective than the other. Both surgical techniques to be tested have been shown to result in clinical improvements in root coverage and soft tissue quality. There is a chance that one procedure may have a risk of increased post-operative discomfort, although there is considerable variability in patient reported discomfort after having received the same treatment with either group.

Regarding procedural risks, due to each subject's physical and dental conditions being unique, the success of tissue grafting cannot be guaranteed. Some discomfort after treatment can be expected. This may include pain, bleeding, inflammation, and soreness. These discomforts can be expected to go away within approximately 48 hours. The treatment site could become infected. If an infection occurs, the study dentist will treat the area.

Risks associated with use acellular dermal matrix (both groups) include a low, theoretical possibility of viral or prion contamination of the materials. No such contamination has ever been reported and ADM has been used in many medical and dental applications. ADM is processed from cadaveric donor skin and all donors are tested for nondetectable levels of HIV and HepC. Furthermore, it is processed using proprietary methods to removal all cells and cellular components (and this is histologically verified for each processing batch) to allow the collagenous and extracellular framework to remain without the cells which may produce antigenicity.

Risks associated with dental anesthesia include injury to nerves, which may cause numbness or tingling of the lips, other teeth, chin, face, and tongue. This is usually temporary but could be permanent. The mouth, lips and tongue may remain numb for up to four hours after the treatment. During this time there may be difficulty eating, drinking, speaking, and smiling.

Some subjects may experience sensitivity or allergy to the anti-bacterial mouth rinse, the local anesthesia, the antibiotics given, or the post-treatment medications prescribed.

A major side effect of the anti-bacterial mouth rinse is staining of the teeth. This stain is similar to stains left by coffee or tea, or by smoking and may be removed by professional teeth cleaning. A less

frequent side effect may include temporary changes in taste. This will disappear once use of the rinse is stopped.

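### Section 6 contradicts itself on what the risks are, and the plan leaves open whether follow-up tissue thickness means repeat bone sounding under local anesthetic

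*Combined protocol and SAP*

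**What the plan says.** **Risk statement.** Section 6 (Risks) begins: "The only risks associated with this protocol involve potential loss of confidentiality and randomization". Later paragraphs of the same section describe procedural risks (pain, bleeding, inflammation, soreness, infection), graft-material risks, allergy, mouth-rinse effects and nerve injury from dental anesthesia. Of the resulting numbness or tingling, the section says "This is usually temporary but could be permanent". It closes by allowing for unknown risks.

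**Tissue thickness at surgery.** Section 2, under the clinical parameters, says that TT1 and TT2 "at the buccal mucosa will be measured during the surgical visit by horizontal transmucosal probing", and specifies "horizontal transmucosal probing (sounding the bone) using an endodontic reamer after local infiltration of anesthetic prior to surgical site preparation". The two points lie 2 mm and 5 mm from the mucosal margin.

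**Tissue thickness at follow-up.** Section 2, follow-up item 4, says: "Tissue thickness (TT1 and TT2) will be evaluated at visits 5, 6 and 7". These visits fall at 3, 6 and 12 months. The item names no method. It adds that measurements from every visit are compared with baseline to follow healing.

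**Thickness as an outcome.** Section 4 (Outcomes Measures) lists change in thickness, assessed by gentle probing within the sulcus and by "level of transparency of the grafted sites at 6 and 12 months". It lists no 3-month thickness outcome and mentions neither anesthetic nor bone sounding.

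**The concern.** There are two problems, and they are connected.

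First, the sentence that opens the risk section excludes every physical risk, and the rest of the section lists several. A reader who relies on the opening sentence comes away with a different account from one who reads on.

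Second, TT1 and TT2 are named variables with one written definition, and that definition is invasive. The same names are scheduled at three visits where no surgery takes place. At surgery the anesthetic is needed anyway, whereas at follow-up it would be given only to take the measurement. Section 6 does not mention that exposure. Section 4, meanwhile, describes a different and gentler assessment for the thickness outcome.

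What is at stake is whether a repeated research procedure is described to those who must judge it, and whether change in thickness is measured in the same way at both ends.

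**Working it through.** The plan gives no count of thickness measurements, so there is no figure of its own to reproduce here. Its one computed figure, 92% power with 20 per group, does not depend on this point.

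**Inputs**
- Participants: 40 (Section 2, study population and group table).
- Follow-up thickness visits: 3, namely visits 5, 6 and 7 (Section 2, follow-up item 4).
- Measurement points per tooth: 2, TT1 and TT2 (Section 2, clinical parameters).
- Treated teeth per patient: 1 to 4 (Section 2, inclusion criteria).
- Time points for the thickness outcome: 6 and 12 months (Section 4).

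**Reading A: the surgical-visit method is reused at follow-up**
- Sessions per patient = follow-up visits = 3.
- Total sessions = 40 × 3 = 120.
- Soundings per visit = 2 points × 1 to 4 teeth = 2 to 8.
- Soundings per patient = 3 × (2 to 8) = 6 to 24.
- Total soundings = 40 × (6 to 24) = 240 to 960.
- Share at 3 months, which matches no Section 4 thickness time point: 40 × 1 = 40 sessions and 40 × (2 to 8) = 80 to 320 soundings.

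These counts assume that every treated tooth is measured at each visit and that all 40 patients are retained. The ends of the range assume one tooth in every patient or four in every patient.

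**Reading B: the Section 4 method is used at follow-up**
- Further infiltrations = 0 and further bone soundings = 0.
- Baseline is a depth to bone at 2 mm and 5 mm from the margin. Follow-up is probing in the sulcus plus a transparency judgement, for which no scale is given. The difference between the two mixes a change in tissue with a change of method.

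**The passages side by side**

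| Place | Method | Time |
|---|---|---|
| Section 2, clinical parameters | Reamer to bone, under infiltration | Surgical visit |
| Section 2, follow-up item 4 | None given; same variable names | 3, 6 and 12 months |
| Section 4 | Probing in the sulcus and transparency | 6 and 12 months |

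No single method and set of times satisfies all three rows.

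**Risk text.** The contradiction between the opening sentence and the later paragraphs holds under either reading. That Section 6 is silent on repeat sounding matters only under reading A.

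**The case against.** The strongest reply is that repeat infiltration is never stated. The definition ties the reamer to the surgical visit, before site preparation. The follow-up item mentions no anesthetic, and the only method given for the thickness outcome is non-invasive. This stands. A reader might infer that the plan requires three further anesthetic sessions per patient; the documents allow that but do not say it, so the range across both readings is 0 to 120 sessions and 0 to 960 soundings. The reply does not settle the matter, because the follow-up item reuses variable names whose only definition is bone sounding, and the gentler method breaks comparability with baseline.

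A second reply is that Section 6 does disclose anesthetic risk, in general terms. This also stands. A reader might infer that patients and the IRB were told the research carries no physical risk. Section 6 as a whole does not say that, and the consent text is not available to check. What is missing is any statement that anesthetic and sounding may recur at follow-up for research.

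A third reply is that the opening sentence means only risks added by the research, since the surgery is described as standard of care. The sentence does not say so, and the section takes up procedural risks alongside the randomization risk without separating care from research. Even on that reading, the sentence is true only if follow-up thickness involves no sounding.

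Finally, a reader might infer that the 3-month measurement has no purpose. Follow-up item 4 gives it one, the course of healing against baseline. It matches no Section 4 outcome, but neither does keratinized tissue width at visits 4 and 5.

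**Conclusion.** The point holds in three parts.

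1. The opening sentence of Section 6 is contradicted by the rest of the section. This is certain from the text.
2. The method and timing of follow-up thickness are inconsistent between Section 2 and Section 4. This is also certain from the text.
3. The extra exposure is conditional. If the surgical-visit method is reused, it is up to 3 research-only infiltrations per patient, up to 120 sessions and 240 to 960 soundings with full retention and all treated teeth measured, and Section 6 does not identify it. If the Section 4 method is used, it is 0, and the cost is instead a change from baseline computed across two methods.

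The sponsor needs to act under either reading. The documents do not establish that repeat sounding will take place, that anesthetic risk is undisclosed, or that the 3-month measurement should be dropped. No sample-size or power figure changes.

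**What to change.** - Delete or correct the opening sentence of Section 6 so that it agrees with the risks listed below it.
- Reconcile the clinical parameters and follow-up item 4 in Section 2 with the thickness outcome in Section 4. State one thickness method, comparable with baseline, and one set of time points. Which method is chosen is for the sponsor.
- If that method involves infiltration and sounding at follow-up, name it in Section 6 as a research procedure and check that the consent text agrees.
- Whether the 3-month measurement stays is for the sponsor and the IRB. If it stays, list it in Section 4 as descriptive, so that the schedule and the outcomes match.

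The cost is protocol wording, plus consent wording if it proves inconsistent. The sample size is unaffected.

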A prospective, randomized clinical trial to compare vestibular incision supraperiosteal tunnel access (VISTA) and sulcular tunnel access root coverage procedures with coronally advanced flap and acellular dermal matrix (ADM) to treat teeth with gingival recession and lack of adequate keratinized tissue. A pilot study.

Study Protocol & Statistical Analysis Plan

NCT03566108

August 31, 2022

[name], MS, Principal Investigator

University of Alabama at Birmingham
Birmingham, AL 35294

A prospective, randomized clinical trial to compare vestibular incision suprapariosteal tunnel access (VISTA) and sulcular tunnel access root coverage procedures with coronally advanced flap and acellular dermal matrix (ADM) to treat teeth with gingival recession and lack of adequate keratinized tissue. A pilot study.

1. Study Protocol 1. Objectives/Specific Aims:

This investigator-initiated study will compare two commonly used soft tissue grafting techniques [vestibular incision suprapariosteal tunnel access (VISTA) vs. sulcular tunnel access root coverage procedures with the uses of acellular dermal matrix (ADM)] to achieve coronal flap advancement and root coverage as well as augmentation of soft tissue at intraoral tooth sites. Research data and daily clinical observations reveal that teeth with gingival recession and a lack of adequate keratinized tissue (KT) are more prone to persistent gingival inflammation, dentinal sensitivity, radicular (root) caries (tooth decay), faster periodontal attachment loss, and compromised plaque control. Soft tissue grafting (by various techniques) aims at changing the quality, quantity and placement of the soft tissue around teeth by covering exposed root surfaces and creating or increasing the zone of keratinized mucosa (KM) surrounding the affected teeth. Both techniques tested have shown good clinical outcomes with regard to root coverage, but clinical reports of the VISTA technique and other similar techniques suggest that patients experience a decrease in site morbidity and discomfort post-operatively. To our knowledge, these 2 types of grafting techniques have not been compared in a prospective trial for differences in clinical (percentage of root coverage, amount of KT increase, tissue thickness increase, and practitioner-assessed esthetics) and patient-centered outcomes (pain, swelling, change in daily activities, and patient-assessed esthetics) in a controlled study.

2. Materials and Method:

Study population:

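### Pain is expected to settle within about 48 hours, but the pain VAS is scheduled only at 1 week and 1 month, so early pain is never scored while it is expected to be present

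*Combined protocol and SAP*

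**What the plan says.** Section 6 (Risks) warns participants of pain and soreness after treatment, along with bleeding and inflammation, and adds: "These discomforts can be expected to go away within approximately 48 hours".

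The timing of the pain measurement is given in two places, and they agree:

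- Section 2 (Materials and Method), follow-up item 5, on the patient survey: "This survey will be performed at visits 2 and 4 using a visual analogue scale". The visit schedule in the same section reads: "The surgical sites will be examined at 1 week (visit 2) and 2 weeks (visit 3) after surgical visits". Visit 4 follows at 1 month.
- Section 4 (Outcomes Measures) lists: "Patient centered outcomes including pain, bleeding, swelling, change in daily activities at 1 week and 1 month postoperatively". It refers to an attached VAS form, which is not part of the text available for this review.

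Visit 1 is the surgery. Section 2 describes no contact between visit 1 and visit 2. The adverse-event review is one of the follow-up visit procedures, so it too first takes place at visit 2. The later patient surveys, at visits 6 and 7, concern esthetics, participation and satisfaction; no pain score is described there.

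Post-operative comfort is part of the reason for the trial. Section 1 says that clinical reports of VISTA and similar techniques point to less morbidity and discomfort after surgery, and it names these targets of comparison: "patient-centered outcomes (pain, swelling, change in daily activities, and patient-assessed esthetics". Section 3 links the renewed interest in vestibular incisions partly to a claimed reduction in discomfort. Section 4 treats the study as a pilot for patient-centered outcomes because there are too few data to size it for them.

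**The concern.** On the protocol's own expectation, most pain occurs in the first two days, and no pain score is taken in that period. What the 1-week score measures depends on how the form asks the question:

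- **Current state.** If patients rate their pain at the visit, scores are likely to be low in both arms. A finding of no difference could then reflect the timing of the measurement rather than similar techniques.
- **Recall.** If patients rate pain since surgery, early pain is captured, but by a single retrospective rating about five days after it is expected to have ended.

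Either way, the trial would report a comparison of post-operative pain with no score taken while that pain is expected. It would also give up something a pilot can readily supply: means and standard deviations of early pain by arm, which a later sample-size calculation would need.

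The concern is confined to early pain. Swelling, bruising, daily activities and healing time could still differ at 1 week.

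**Working it through.** **The plan's own calculation.** The only computed figure is the power statement in section 4: 20 per group, margin -1.0, true difference 0.1, SD 1.0, one-sided alpha 0.025. The noncentrality is (0.1 + 1.0) / (1.0 × √(2/20)) = 3.48 with 38 degrees of freedom, and the noncentral t gives 92.4%, which matches the stated 92%. The present point does not depend on it.

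**Inputs for the timing check**

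| Input | Value | Source |
|---|---|---|
| Expected duration of discomfort | about 48 h | Section 6 |
| First pain VAS | visit 2, 1 week | Sections 2 and 4 |
| Second pain VAS | visit 4, 1 month (taken as 30 days) | Sections 2 and 4 |
| Contacts between surgery and visit 2 | none described | Section 2 |
| Patients | 40, 20 per arm | Section 2, group table |

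**Timing**

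1. First score: 7 × 24 = 168 h after surgery.
2. Gap after expected resolution: 168 − 48 = 120 h, or 5 days. As a ratio, 168 / 48 = 3.5 times the expected duration.
3. Second score: 30 × 24 = 720 h, and 720 / 48 = 15 times the expected duration.
4. Pain time points within 48 h: 0 of 2.

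**Sensitivity to the 48-hour figure.** It is approximate. If discomfort lasted twice as long (96 h, an assumption), the first score would still come 168 − 96 = 72 h, or 3 days, after it had settled.

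**Size of the remedy.** Four scores per patient (evening of surgery, days 1, 2 and 3) give 4 × 40 = 160 scores, or 4 × 20 = 80 per arm. Three of the four fall within about 48 h.

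The documents give neither an expected VAS difference nor a VAS standard deviation, so the effect on precision or power for pain cannot be calculated.

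**The case against.** The strongest reply is that the harm depends on a form that was not seen. If the 1-week VAS asks about the period since surgery, early pain is recorded, and what remains is a preference for several prospective ratings over one retrospective one. The survey also asks about daily activities, which suggests a question about an interval. This is a fair limit. It is why the conclusion is that no contemporaneous score is described, not that early pain goes unrecorded. Under recall the case is weaker but remains: section 6 itself notes that ratings vary widely among patients given the same procedure, which favours more than one early rating.

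The 48-hour figure is wording for a risk section, not a design assumption, and it does not mean that nobody has pain at day 7. That stands. It is nevertheless the only expected duration the documents give, and doubling it does not bring the first score inside the painful period.

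The documents also do not contradict one another: the outcome is listed at 1 week and 1 month and is scheduled at those times. Nor does a first adverse-event review at visit 2 prevent patients from reporting earlier events. Both points are correct. This is a weakness in a design choice, not an inconsistency.

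Finally, early diary scores have difficulties of their own. Patients take pain relief, numbness may last up to four hours and could affect a first-evening score, day 3 lies outside the 48-hour period, and some pages will come back incomplete. These points bear on how the summary is defined. Apart from missing pages, they do not undermine a randomised comparison of pain as experienced after each technique.

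**Conclusion.** The concern holds. None of the 2 scheduled pain scores falls within the roughly 48 hours in which the protocol expects pain, and the first comes about 5 days later. This rests on two things: the approximate duration in section 6, and the absence of any described diary, call or visit before visit 2. Whether an early difference would be missed, or only measured by a single recalled rating, depends on the wording of the VAS form and cannot be settled from the text.

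The change is worth making because pain is a named outcome, early comfort is part of the rationale, and the remedy is cheap. The primary analysis and the sample size do not change.

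**What to change.** Add a one-page take-home form with the same pain VAS for the first days after surgery, for example the evening of surgery and days 1, 2 and 3. It can go out with material already handed over at surgery, where section 2 states that "prescriptions for relief of post-surgical discomfort, follow-up antibiotics and written home care instructions will be provided". Patients return it at visit 2.

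Pre-specify one summary for the comparison between arms, such as the mean over days 0 to 3, or over the three scores within about 48 hours if the early period alone is of interest. Report it as exploratory, in keeping with the pilot status in section 4, and give the number of complete pages per arm. A space on the page to note pain relief taken would help interpretation. Keep the 1-week and 1-month surveys as planned.

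Two small text edits can be made at the same time. State the recall period of the attached VAS form, and align the survey items: section 2 lists bruising where section 4 lists bleeding.

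The cost is one form, entry of up to 160 scores, and some incomplete pages. No extra visit or staff is needed.
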